RANDOMIZED CLINICAL TRIAL OF DIATHERMY VERSUS SCALPEL IN ABDOMINAL WALL INCISION DURING REPEAT CESAREAN DELIVERY

Principal Investigator: [name].

Sub-Investigator: [name] [name], PGY3.

Department of Obstetrics and Gynecology, Odessa, TX

INTRODUCTION / BACKGROUND

Cesarean delivery (CD) is the operative mode of the delivery, which includes laparotomy (skin incision) and hysterotomy (uterine incision) in order to facilitate the delivery of the newborn. In the modern obstetric practice in the United States one in three women who gave birth did so by CD. (1). Cesarean birth can be life-saving for the fetus, the mother, or both in certain cases. The rate of primary CD has increased and more women prefer elective repeat cesarean delivery (ERCD) (2). This increased rate of cesarean deliveries is associated with the short- and long-term maternal complications (3) such as RBC transfusion (2). Among approaches used to reduce the rate of the postoperative complications are prophylactic administration of antibiotics (4) and improvement of surgical techniques (5). In particular, the improvement of surgical technique could contribute to more than two-fold decrease in post-operative morbidity (5). The application of techniques of the abdominal incision during CD is associated with hysterotomy approaches and subsequently maternal morbidity in specific patient populations (6).

During surgical procedures, one of the widely used approaches to decrease blood loss, surgery time and thus post-operative complications is tissue dissection by electrosurgery, which is defined as the process of applying high-frequency electric current to the tissues to cut, coagulate, and desiccate (7). After the introduction of electrosurgery into the practice of surgery in 1926 by William T Bovie and [name] W Cushing (8), it has since become a powerful tool in different surgical subspecialties (9)(7).

Electrosurgical instruments are widely used for tissue dissections and to control bleeding, as an easy and safe surgical approach, but their use in making skin incisions is limited. The major purported disadvantages of electrosurgical skin incisions are fears of deep burns; with resultant scarring (10), slower wound healing , and increased postoperative pain . However, recent meta-analyses showed decreased incision time, blood loss and post-operative pain with no significant difference in wound infection rates or scar (13)(14).

With improved techniques of electrosurgery, several randomized trials - the gold standard of clinical research, were performed. A randomized double blind study (15) performed in 369 patients, showed that diathermy incision is superior compared to scalpel incision with reduced incision time, less blood loss and reduced early postoperative pain. The same advantages have been reported using advanced diathermy technology by Lee et al(16). The mechanism of these positive effects of cutting electrosurgery is that the skin is cut with an electrode delivering pure sinusoidal current, which allows tissue cleavage by rapid cell vaporization without damage to surrounding areas; this may explain the absence of tissue charring and the subsequent healing with minimal scarring (17).

Taking together, the recently published advantages of diathermy in the skin incision could be extremely useful in preventing complications and decreasing maternal morbidity associated with CD. However, there are no clinical trials comparing scalpel and diathermy in the population of pregnant patients undergoing CD. To perform such trials will have direct translational value. In situations of emergency cesarean sections, as an example, it will provide important information on which method will be fastest with the least amount of blood loss.

OBJECTIVE

The objective of this study is to compare scalpel vs. diathermy in abdominal wall incision, in pregnant patients undergoing repeat elective cesarean delivery.

HYPOTHESIS

We hypothesize that the abdominal wall incisions made by diathermy compared to scalpel during repeat cesarean delivery will have less incision time, as well as less blood loss. Further we hypothesize that the use of diathermy, compared with scalpel will not increase post-operative pain.

METHODS

- 1) This is a randomized prospective study in women undergoing elective repeat cesarean delivery or repeat unplanned non-emergent cesarean delivery at Medical Center Hospital in Odessa Texas.
- 2) After informed consent is obtained, women undergoing cesarean delivery will be randomized into two groups:

Group One

Will undergo diathermy to incise the entire abdominal wall, which includes skin, subcutaneous tissue, rectus muscle until the peritoneal cavity is visible.

Group Two

Scalpel will be used to achieve the same aims

- 3) Only patients undergoing elective repeat cesarean delivery will be enrolled, this will decrease the likelihood of introducing bias into the outcome measures, as well as it will make the population more uniform.
- 4) A standardized abdominal wall incision will be made with either diathermy in cut mode or scalpel. Diathermy will be set in a cut mode with standard setting as per surgeon's preference. All patients in the study will get standard skin incision in terms of length and depth which will be marked by a ruler.
- 5) Incision start and stop time will be recorded by a "timer". A digital wall clock in the OR will be used to establish time. The timer will instruct the surgeon to "cut". The timer will record the time. Once the surgeon reaches the abdominal peritoneum, they will announce "stop". The timers will record the time. The incision time will be the difference between the "cut" and "stop" times. These times will be recorded in units of seconds.

- 6) Along the incision depth the bleeding points will be mopped with sponge laps, no suction will be used and total blood loss will be calculated by weighing the laps.
- 7) Blood loss will be recorded as follows: A "used" lap sponge will weighed. A "fresh" lap sponge will be weighed. These weights will be recorded. Blood loss will be calculated as the differences in these two weights. These weights will be recorded in grams.
- 8) As per standard of care spinal or epidural anesthesia will be administered by certified registered nurse anesthetist (CRNA). Post-operative pain will be managed as follows: 1) 300 micrograms of Morphine sulfate will be injected through then spinal needle or epidural catheter at the beginning of the case. 2) 30 milligrams of Toradol will be injected IM, in the left thigh, at the conclusion of the case. 3) 10 mg hydrocodone/325mg acetaminophen 1-2 tablets, per oral, every 4-6 hours, PRN pain.
- 9) Post-operative pain will be measured by a Numeric Pain Rating Scale (see below) scored as 0= no pain, up to 10= worst possible pain. This score will be assessed daily by resident staff at 6:00 to 7:00 AM from post –op day 1 until hospital discharge.
- 10) As per standard MCH protocol, within one hour preoperatively, Ancef 2-3gms will be administered IV. If the patient is Penicillin allergic, she will receive either 900 milligrams of Clindamycin or 1gram of Vancomycin.

OUTCOMES-

Both groups will be assessed for

Primary outcomes:

1. Incision time
2. Blood loss

Secondary outcome:

1. Postoperative pain

SELECTION OF PATIENTS

Inclusion Criteria -

1. Multiparous pregnant women 18 – 45 years.
2. Gestational ages 37 weeks to 41 weeks,
3. Undergoing repeat elective or repeat unplanned non-emergent cesarean deliveries.

Women with medical comorbidities like hypertension, diabetes complicating pregnancy, pregnant women with or without prenatal care, and multiple gestations will also be included.

Exclusion Criteria –

1. Informed consent can't be obtained in a manner that allows for no impression of undue influence/pressure or sufficient time for patient to consider participation.
2. Primary Cesarean deliveries – as these can bias the selection.
3. Skin conditions such as infections, psoriasis, and eczema.

RECRUITMENT PLAN

Patients from University Women's Health Centre (Texas Tech OBGYN clinic) and also from Medical Center Hospital, Odessa, Texas will be recruited. Potential participants will be identified by a member of the study team or clinic/hospital personnel caring for the patient. In the latter case, study personnel will be contacted to meet the patient after the patient has expressed an interest in learning more about participation. All the participants will have the study procedures, risks, benefits and alternatives explained by a member of the study team.

Once informed consent is obtained they will be randomized with 1:1 allocation by a computer generated randomization process. Since the annual rate of cesarean

Protocol version: 1.0

Page 5 of 11

deliveries in the above-mentioned centers ranges 150 to 175, we expect to enroll a total of 100 patients, and we will allocate 50 patients to each group. Assuming a significance level of 0.05 and a power of 80%, and observing that there is a single measurement and null attrition rate, we will be able to detect at least moderate effect sizes ($d=0.50$) when performing independent means comparisons.

RISKS:

Diathermy –

- A. Possibility of poor wound healing,
- B. There are concerns that large or excessive scars may form,
- C. Unanticipated burns on skin, subcutaneous tissues and other vital organs.

Scalpel –

- A. Injury to the major blood vessels.
- B. Injury to the vital organs.
- C. Excessive bleeding

From the review of recent literature there are some concerns raised regarding the use of diathermy for skin incisions (10, 11, 12). However, we believe that the use of cutting diathermy, as described in our protocol, does not increase patient risk within the study group. First, there is a concern that diathermy, while making skin incisions, may increase the risk of wound complications, as well as delayed wound healing. However these studies differ from ours in a number of ways: A) Most studies claiming increase in risk examine midline abdominal incisions, and our study employs Pfannenstiel skin incision. B) In some studies it is unclear if pure cut mode was employed. The use of a blend mode will cause more lateral spread of current. This may increase the amount of tissue damage, thus promoting wound complications. Our study will employ diathermy only in pure cut mode in a standard setting as per surgeon's preference. A recent Cochrane review, which includes only randomized trials (the highest form of scientific inquiry), found no significant difference in wound complications between scalpel and diathermy (18).

Second, there has been a case report of a severe burn injury on patients back while utilizing diathermy during cesarean delivery (19). The purported mechanism for this burn was an interaction between diathermy and amniotic fluid (19). However in our study, cutting diathermy will be used only in incision of skin, subcutaneous fat and rectus fascia. This use precludes any interaction between diathermy and amniotic fluid.

ADVERSE EVENTS REPORTING:

Any event deemed as an Adverse Event that is possibly related or unexpected to the study will be assessed at each data gathering point and will be reported to the TTUHSC IRB as described in the IRB policies and procedure manual. Monitoring of adverse events will start on the day of surgery.

BENEFITS – There are no guarantees of any benefit to study participants. However, participants may have potential benefits of using electrosurgery which include reducing the amount of blood loss, dry and rapid separation of tissues. For surgeons, there is a reduced risk of accidental cut injuries.

DATA ANALYSIS :

Distributions of operative time, blood loss and post-operative pain will be tested for normal distribution. Student's T test or the non-parametric equivalent will be used to compare these outcomes between the study and control group. Significance level will be set at 0.05.

DATA MONITORING PLAN:

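### The pain hypothesis is one of no increase, but the planned difference test has no margin, confidence-interval rule or named pain score, so it cannot support that hypothesis unless pain is significantly lower

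*Combined protocol and SAP*

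**What the plan says.** The Hypothesis section predicts less incision time and less blood loss with diathermy, then makes a different kind of statement about pain, the only secondary outcome: "Further we hypothesize that the use of diathermy, compared with scalpel will not increase post-operative pain".

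The Data Analysis section treats all three outcomes alike. After a normality check, "Student's T test or the non-parametric equivalent will be used to compare these outcomes between the study and control group", and "Significance level will be set at 0.05". Neither this section nor any other gives a non-inferiority margin, a confidence-interval rule or the sidedness of the test.

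Methods item 9 sets the schedule for the 0–10 pain scale: "This score will be assessed daily by resident staff at 6:00 to 7:00 AM", from post-operative day 1 until discharge. Collection times are therefore defined. The day or summary to be compared is not. The sample-size paragraph under Recruitment Plan assumes one measurement per woman, which does not fit daily scoring and does not identify a score.

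The Results section, written as an expectation, predicts less pain with diathermy. The document thus makes two different pain claims.

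**The concern.** A hypothesis of no increase needs a limit on how much worse pain may be before the claim fails, and an analysis that can exclude differences beyond that limit. A difference test does neither. If it is non-significant, a pain increase may be absent or merely undetected.

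The Introduction lists "increased postoperative pain" among the purported disadvantages of electrosurgical skin incision, although it goes on to cite meta-analyses showing less pain. Readers will therefore look to this outcome for reassurance, and a non-significant p-value could be taken as that reassurance without supporting it.

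The unnamed time point adds a second problem. With several daily scores, two test families and unstated sidedness, the comparison could be chosen after the data are seen. Scores from later days also come only from women still in hospital, so those comparisons no longer include everyone randomised.

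**Working it through.** **Inputs from the documents.** 50 women per group, significance level 0.05, power 80%, d = 0.50 (Recruitment Plan); t test or rank equivalent (Data Analysis). No pain SD or margin is given, so results are in SD units. True increases, margins and SDs in scale points below are assumptions that show a range. All figures are for the t test.

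**The plan's own figure.** For d = 0.50 and 50 per group, t-test power is 79.9% at one-sided 0.05 and 69.7% at two-sided 0.05. The stated 80% therefore reproduces only one-sided. Since sidedness is not stated, both readings are shown for the test.

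**Precision.** Degrees of freedom = 50 + 50 − 2 = 98. Standard error of the difference = √(2/50) = 0.20 SD. The two-sided 95% CI half-width is t(0.975, 98) × 0.20 = 1.984 × 0.20 = 0.397 SD. At assumed SDs of 2, 2.5 and 3 points this is about 0.8, 1.0 and 1.2 points.

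**Chance that a true increase is non-significant.** For a true increase δ (in SDs), the t statistic is noncentral t with 98 df and noncentrality δ/0.20. The two-sided test is non-significant when |T| < 1.984. The one-sided test, directed at an increase, is non-significant when T < 1.661.

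| True increase | Noncentrality | Two-sided 0.05 | One-sided 0.05 |
|---|---|---|---|
| 0.3 SD | 1.5 | 68% | 56% |
| 0.4 SD | 2.0 | 49% | 37% |
| 0.5 SD | 2.5 | 30% | 20% |

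**Chance of a supporting result when pain is equal.** Only significantly lower pain supports the hypothesis through this test. At δ = 0 its probability is 2.5% two-sided, or 5% with a one-sided test directed at a decrease.

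**What a just non-significant increase allows.** An observed increase of 0.397 SD is at the edge of two-sided significance. Its upper 95% limit is 0.397 + 0.397 = 0.79 SD.

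**What a confidence-interval rule would do.** The upper limit lies below a margin m when T < −1.984, with noncentrality (δ − m)/0.20.

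- At δ = 0, for m = 0.4, 0.5 and 0.6 SD, the probability is 0.508, 0.697 and 0.844.
- At δ = 0.3, 0.4 and 0.5 SD with m = 0.5 SD, it is 0.166, 0.071 and 0.025.
- At the same increases with m = 0.75 SD, it is 0.606, 0.410 and 0.235.

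A tight margin is often inconclusive when pain is equal. A wide one often passes real increases.

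**The case against.** The strongest reply is that the Results section expects less pain with diathermy, and the Introduction cites evidence of less pain, so a difference test suits the authors' expectation. That is fair as far as it goes, and it means the two pain statements need reconciling. It does not rescue the stated hypothesis. Even at a true reduction of 0.3 SD, the test shows significantly lower pain in only 32% of trials two-sided or 44% one-sided, and at no difference it hardly ever does.

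Other points limit the concern without removing it:

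- Pain is secondary, and the document never says that a non-significant result will be read as no increase. That reading is a risk, not a stated rule.
- The percentages are general properties of a 50-per-group comparison. Length of stay is not given, so the effect of discharge on later scores cannot be sized.
- The two-sided 95% CI is a convention. With a 90% CI (one-sided 0.05), margins of 0.4, 0.5 and 0.6 SD would be met in 63%, 80% and 91% of trials at no true difference. The inconclusive share at 0.5 SD would then be 20%, not 30%.
- Methods item 8 allows tablets as needed for pain. These could draw the groups' scores together, so a margin rule on scores alone could be met too easily. This stands as a caution in interpreting the result.

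**Conclusion.** The concern holds, with high confidence. The stated pain hypothesis and the stated analysis do not match: unless pain is significantly lower with diathermy, the planned test cannot support the hypothesis, and it would miss a true increase of 0.3 to 0.5 SD in 68% to 30% of trials two-sided, or 56% to 20% one-sided. The gap in the pain time point is confined to analysis, since collection times are given.

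These figures assume 50 women analysed per group and a t test. The true increases and margins are illustrative, and the conversion to scale points rests on assumed SDs. Neither primary outcome is affected. This should be fixed, but it does not call for a larger trial.

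**What to change.** Before analysis, amend the Hypothesis and Data Analysis sections as follows.

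1. Name one pain summary to which every woman contributes. One example is the first scheduled score, on post-operative day 1, assuming no discharge before it. This score is the closest to the analgesia given at surgery (item 8: "Morphine sulfate will be injected through then spinal needle or epidural catheter at the beginning of the case"), and time since surgery will vary between women. Say so in the report.
2. Report the diathermy-minus-scalpel difference with a two-sided 95% CI. State in advance whether it is a difference in means or a rank-based shift, because the margin must apply to the same quantity.
3. Claim no increase only if the upper limit is below a clinically justified margin fixed in advance. Do not choose the margin for power: the 0.75 SD results above show how often a wide margin passes a real increase.
4. If no margin can be justified, report the CI and drop the claim of no increase. Pain could then be restated as a difference comparison in line with the Results section. Either way, reconcile the two sections.
5. Treat the other days as descriptive.

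The cost is wording and analysis only, on scores already planned. The downside is that the pain conclusion may be inconclusive: 1 − 0.697, or about 30% of trials, with a 0.5 SD margin even if pain is truly equal. A day 1 score also says little about later pain.

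### Nothing requires the operator to be named before the arm is known or recorded with the diathermy setting, and the tests of two operator-dependent primary outcomes have no operator term

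*Combined protocol and SAP*

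**What the plan says.** On the setting, METHODS item 4 states "Diathermy will be set in a cut mode with standard setting as per surgeon's preference". The discussion under RISKS repeats it: "Our study will employ diathermy only in pure cut mode in a standard setting as per surgeon's preference". No value is given, and nothing says that the setting used in a case is written down.

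On the incision, item 4 adds "All patients in the study will get standard skin incision in terms of length and depth which will be marked by a ruler". Length and depth are therefore standardised in both arms, and RISKS adds the incision type (Pfannenstiel) and pure cut mode.

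On the operator, METHODS item 5 has a timer tell the surgeon to start and has the surgeon announce arrival at the peritoneum, which ends the incision time. Number of operators, grade, experience, and how or when they are assigned are not stated. Items 5, 7 and 9 describe recording of times, lap weights and pain scores. They do not mention operator or setting.

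On allocation, RECRUITMENT PLAN states "Once informed consent is obtained they will be randomized with 1:1 allocation by a computer generated randomization process". No stratification is mentioned. On analysis, DATA ANALYSIS states "Student's T test or the non-parametric equivalent will be used to compare these outcomes between the study and control group".

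**The concern.** Both primary outcomes are products of one person's hands over a short interval: time from first cut to peritoneum, and blood mopped along the way. That person necessarily knows the arm and also calls the end of the timed interval.

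Randomising patients balances operators only if the operator is settled without regard to the arm. Allocation follows consent, and nothing requires the operator to be named first, so a team could match operator to instrument once the arm is known. There is a plausible motive: the INTRODUCTION says that electrosurgical instruments are little used for skin incisions, so familiarity may differ between the two techniques. If matching happened, a difference in skill would appear as a difference between instruments. Without a trial record of the operator, the analysis could neither show it nor correct it.

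The setting raises a separate and smaller matter. It concerns what treatment the diathermy arm actually received, and whether another centre could reproduce it.

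**Working it through.** **The plan's own figure.** RECRUITMENT PLAN gives 50 per arm, significance level 0.05, 80% power, d = 0.50 and no attrition; sidedness is not stated. With the noncentral t distribution, 50 per arm and d = 0.50 give 79.9% power one-sided and 69.7% two-sided. The stated 80% is therefore reproduced only one-sided. Two-sided tests are used below, so the reference power is 69.7%.

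**Inputs that are assumptions.** The documents give no skill gap and no operator mix. Assume two operator classes whose mean incision times differ by g, in units of the SD within a class, with g from 0.5 to 1.0. The true instrument effect is zero except in the power calculation.

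**Case A: operator chosen after the arm is known.** Let the skilled share be p1 in one arm and p2 = 1 − p1 in the other.

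- Bias = (p1 − p2) × g
- SD within an arm = √(1 + g² × p1 × p2)
- Noncentrality = bias / (SD × √(2/50)) = bias / (SD × 0.2)

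For 60/40 and g = 1.0: bias = 0.2 × 1.0 = 0.20; SD = √(1 + 0.24) = 1.114; noncentrality = 0.20 / (1.114 × 0.2) = 0.898. The two-sided t test at 5% then rejects in 14.4% of trials. The table sets this formula beside a simulation of 20,000 trials per row, whose standard error near 5% is √(0.05 × 0.95 / 20,000), about 0.15 points.

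| Split | g | Bias (SD within class) | Rejection, simulated | Rejection, formula |
|---|---|---|---|---|
| 55/45 | 0.5 | 0.05 | 5.4% | 5.7% |
| 55/45 | 1.0 | 0.10 | 7.1% | 7.3% |
| 60/40 | 0.5 | 0.10 | 7.9% | 7.7% |
| 60/40 | 1.0 | 0.20 | 14.2% | 14.4% |
| 70/30 | 0.5 | 0.20 | 16.2% | 16.2% |
| 70/30 | 1.0 | 0.40 | 43.7% | 43.7% |

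The 70/30 rows show how steeply the error rises. Nothing in the documents suggests a split of that size.

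**Case B: operator set independently of the arm.** With an expected 50/50 mix in each arm, simulated rejection is 5.2% (g = 0.5) and 5.1% (g = 1.0), and mean bias is about zero. The cost is power. For a true effect of 0.5 within-class SD, leaving operator level out inflates the SD to √(1 + 0.25g²):

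- g = 0.5: SD = 1.031, effect = 0.5 / 1.031 = 0.485, power 67.1%
- g = 1.0: SD = 1.118, effect = 0.5 / 1.118 = 0.447, power 60.0%
- Adjusted for level: effect 0.5, power 69.7% (the degree of freedom spent on the term does not change the first decimal)

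Adjustment therefore recovers 2.6 to 9.7 points of power under these assumptions.

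**The case against.** The strongest reply is that systematic bias needs a behaviour that no section describes, namely picking the operator after seeing the arm. That is correct. If the operating list is set independently, randomisation protects the comparison, as Case B shows. What remains is that the protocol does not prevent the behaviour, and that power is lost in either case.

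Several stronger readings are tempting and are not supported:

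- A reader might infer that the choice of operator is left to the surgeon. Only the diathermy setting is. On the operator the documents are silent.
- A reader might treat variation in the setting as a source of imbalance. The setting exists in one arm only, so it cannot differ between arms. It is part of the diathermy treatment as delivered, and mode, length and depth are fixed.
- A reader might count chance differences in operator mix as inflating the error. With a 50/50 mix, a chance gap of 20 points or more arises in about 5.7% of trials, but the 5% test level already allows for it.
- A reader might take the randomisation to be unrestricted. The text says only 1:1 and computer generated; the method could be blocked.
- A reader might conclude from the PGY3 sub-investigator that trainees make the incisions. The only task METHODS gives resident staff is pain scoring.
- A reader might say that the operator can never be identified later. Operative notes may name the surgeon, and the DATA MONITORING PLAN refers to source documents. The narrower statement stands: no section brings the operator into the trial data or the analysis.

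It is also fair to say that the two descriptions of the setting may simply mean each surgeon's usual cut setting. That makes it loose wording more than a flat contradiction, but a reader cannot tell which was meant.

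**Conclusion.** The point holds as an inexpensive improvement to design and analysis. It is not a demonstrated bias. The protocol leaves open a route by which operator skill could be read as an instrument effect, and its unadjusted test discards information on a probable source of variation in both primary outcomes.

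The size is conditional throughout. With selection after allocation and a gap of 0.5 to 1.0 SD, two-sided error is about 5.4% to 7.1% at 55/45, barely above nominal at the lower end, and about 8% to 14% at 60/40. The 60/40 bias of 0.10 to 0.20 SD compares with a planned detectable effect of 0.50. Without such selection, error stays near 5% and the cost is power: 67.1% to 60.0% unadjusted against 69.7% adjusted. Two operator classes, an even overall mix and the size of the gap are all assumptions.

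**What to change.** 1. Record the level and coded identity of the person who will make the incision before the allocation is opened. Where the operator is not known at consent, as may happen for patients recruited in clinic or for unplanned deliveries, open the allocation at the time of surgery.
2. Require that operator to make the incision, and log any change as a deviation.
3. Include operator level in the analysis of incision time and blood loss, for example by a linear model with arm and level, or a rank test stratified by level if the data are not normal. Stratifying the randomisation by level is optional.
4. Record the setting used in each diathermy case, to define the treatment delivered.
5. Reconcile the two descriptions of the setting, as standard and as the surgeon's choice, in METHODS item 4 and under RISKS. No particular setting is proposed here.

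The cost is a few fields on the operative data sheet and one model term or stratum. The main inconvenience is that allocation may have to be opened later than consent. Last-minute operator changes also become deviations to be logged.

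### No masking of the patient or the pain scorer is described, so biased scoring could hide a real increase in pain with diathermy

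*Combined protocol and SAP*

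**What the plan says.** METHODS item 9 defines the instrument: "Post-operative pain will be measured by a Numeric Pain Rating Scale (see below) scored as 0= no pain, up to 10= worst possible pain". It then names the collector: "This score will be assessed daily by resident staff at 6:00 to 7:00 AM", from the first postoperative day until discharge. OUTCOMES lists incision time and blood loss as primary and pain as the only secondary outcome.

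HYPOTHESIS states the pain claim: "the use of diathermy, compared with scalpel will not increase post-operative pain". RESULTS goes further and expects pain to be lower with diathermy.

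The title block reads "Sub-Investigator: [name] [name], PGY3", so the study team appears to include a resident.

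METHODS item 1 describes the design only as follows: "This is a randomized prospective study in women undergoing elective repeat cesarean delivery or repeat unplanned non-emergent cesarean delivery". The one mention of blinding is in INTRODUCTION / BACKGROUND and concerns a cited trial: "A randomized double blind study (15) performed in 369 patients". People outside the study team appear only in DATA MONITORING PLAN, for quality assurance and not for scoring outcomes. METHODS item 8 has the women under spinal or epidural anaesthesia.

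**The concern.** Incision time is read from a clock and blood loss from a scale. Pain is the most subjective of the three outcomes, and knowledge of the arm can enter it in two ways: through the woman's own expectation, and through how the question is asked and the answer recorded. The plan closes neither route.

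The background section lists more postoperative pain among the purported reasons why diathermy is little used on skin. This outcome is therefore the trial's only patient-reported evidence on that worry. The study team has recorded a belief about the result, and the group that collects the scores may overlap with that team. A lean of the ratings towards diathermy would make a true increase harder to see, and a null result would then be read as confirming the hypothesis.

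**Working it through.** **Where masking could have been stated.** METHODS items 1, 2 and 9, RECRUITMENT PLAN (randomisation), DATA ANALYSIS and DATA MONITORING PLAN were checked. None says that the patient, the pain collector or the analyst is unaware of the arm. Item 9 does not require the collector to be independent of the operation or of the study team.

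**Inputs from the documents.** RECRUITMENT PLAN gives 50 per group, significance level 0.05 (sidedness not stated), 80% power and d = 0.50. DATA ANALYSIS gives Student's t test or a non-parametric equivalent.

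**Inputs assumed.** The documents give neither the bias nor the SD. The bias favouring diathermy is taken as b = 0.1, 0.2 or 0.3 SD, and the SD as 1.5 to 2.5 points. One score per woman is analysed.

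**Step 1: the plan's own figure.** The standard error of the difference in SD units is √(2/50) = 0.2, so the noncentrality is 0.50/0.2 = 2.5 on 98 degrees of freedom. Power is 79.9% one-sided and 69.7% two-sided. The stated 80% therefore reproduces only as a one-sided 0.05 test. That is a separate matter, and both versions are shown below.

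**Step 2: a true increase partly hidden by bias.** If diathermy truly raises pain by 0.50 SD and scoring favours diathermy by b, the observed mean difference is 0.50 − b. The noncentrality is then (0.50 − b)/0.2. The power columns give the chance of a significant result in the harmful direction.

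| b (SD) | b in points (SD 1.5 / 2.0 / 2.5) | 0.50 − b | Noncentrality | Two-sided 0.05 | One-sided 0.05 |
|---|---|---|---|---|---|
| 0 | 0 | 0.50 | 2.5 | 69.7% | 79.9% |
| 0.1 | 0.15 / 0.20 / 0.25 | 0.40 | 2.0 | 50.8% | 63.4% |
| 0.2 | 0.30 / 0.40 / 0.50 | 0.30 | 1.5 | 31.8% | 43.8% |
| 0.3 | 0.45 / 0.60 / 0.75 | 0.20 | 1.0 | 16.6% | 25.7% |

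Hand check of the two-sided column by the normal approximation, Φ(noncentrality − 1.96): Φ(0.54) = 0.705, Φ(0.04) = 0.516, Φ(−0.46) = 0.323, Φ(−0.96) = 0.169.

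**Step 3: other true increases, two-sided 0.05, for b = 0, 0.1, 0.2, 0.3.** A true increase of 0.3 SD gives 31.8%, 16.6%, 7.1% and 2.5%. A true increase of 0.7 SD gives 93.4%, 84.4%, 69.7% and 50.8%. The loss is present throughout.

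**Step 4: what remains without bias.** The 95% confidence interval for the difference has half-width 1.984 × 0.2 = 0.397 SD. That is 0.60, 0.79 or 0.99 points for an SD of 1.5, 2.0 or 2.5. No margin is given against which to judge it.

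**The case against.** Several stronger readings are tempting, and the documents do not support them.

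- **The operating or investigating resident scores her own patients.** METHODS speaks only of the surgeon. No section says that residents operate or that the sub-investigator collects scores. The overlap is possible and not excluded, but it is not documented.
- **The trial is open-label and patients are told their arm.** The protocol is silent on masking and does not declare an open design. The consent pages and one figure are not available, so what patients are told is unknown.
- **The cited double-blind trial proves that blinding is feasible here.** It was in general surgery. The protocol does not say who was blinded, how, or under what anaesthesia. These women have spinal or epidural anaesthesia and may learn the arm in the operating room.
- **The harm is an inflated false-positive rate.** One could assume a 0.5-point bias with an SD of 1.5 to 2.5 points and compute a two-sided false-positive rate of 17% to 38%. With bias towards diathermy, those would almost all be false findings of less pain. The hypothesis at risk is that pain is not increased, so the relevant measure is the lost chance of seeing an increase.

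It can also be said that pain is secondary, that the rating is the patient's own, and that bias need not favour diathermy. RISKS lists burns and scarring for that arm, which could push a woman's rating the other way. A further objection is that masking is not the main obstacle to the pain claim, because the planned test has no margin.

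All of this limits the strength of the point but does not remove it. The plan leaves a subjective outcome open to people who may know the arm, and the collector's independence can be secured whatever the patient knows.

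**Conclusion.** The concern holds as a weakness in a secondary outcome that should be corrected. The protocol describes no masking of the patient or of the pain scorer, and it does not stop someone who knows the arm from eliciting the score.

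On the assumed figures, a true increase of 0.50 SD would be detected with probability of about 70% without bias and about 51%, 32% or 17% with a bias of 0.1, 0.2 or 0.3 SD (two-sided 0.05, 50 per arm, one score per woman). The size and direction of the bias are assumptions, so the calculation shows how sensitive the trial is and does not estimate what will happen.

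Masking is necessary for a credible pain comparison but not sufficient for the stated claim. An ordinary difference test with no margin cannot establish that pain is not increased, even with unbiased scores.

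**What to change.** Amend METHODS item 9 to say:

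- the patient marks the printed 0-10 scale herself;
- study staff do not disclose her arm until after her last pain score;
- where she cannot mark it herself, the score is taken by a resident who was not in her operation;
- the record shows who collected each score and whether that person knew the arm.

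Report patient masking as a limitation, because it will be imperfect under spinal or epidural anaesthesia. If scores have already been collected, report who collected them and whether they knew the arm.

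The cost is protocol wording, one added field on the record and minor scheduling. No extra patients or visits are needed. Self-marking does not depend on which resident is available. Only the fallback does, and the documents give no resident numbers or rota from which to judge it.

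The change alters no stated sample-size figure. The missing margin for the no-increase hypothesis needs its own correction.
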